## 2 SELECTION OF SITES/CLINICIANS

The trial sponsor (Imperial College London) has overall responsibility for site and investigator selection.

### 2.1 SITE/INVESTIGATOR INCLUSION CRITERIA

To participate in the RIVER trial, investigators and clinical trial sites have fulfilled a set of basic criteria that have been agreed by the RIVER Project Management Group (PMG) and are defined below.

The clinical sites included in this protocol have previously been part of a successful collaborative effort to enrol individuals presenting with acute HIV infection. The CHERUB collaboration (Collaborative HIV Eradication of viral Reservoirs: UK BRC) is a unique collective effort between the 5 key Academic Health Science Centres (AHSC) in the UK who have been working together for the past 3 years to develop laboratory and clinical expertise in the field of HIV cure research.

#### 2.1.1 PRINCIPAL INVESTIGATOR'S QUALIFICATIONS & AGREEMENTS

1. The investigator should be qualified by education, training, and experience to assume responsibility for the proper conduct of the trial at their site and should provide evidence of such qualifications through an up-to-date curriculum vitae and/or other relevant documentation requested by the Sponsor, the REC, and/or the regulatory authority.
2. The investigator should be thoroughly familiar with the appropriate use of the investigational product, as described in the protocol, in the current Investigator Brochure, in the product information and in other information sources provided by the Sponsor.
3. The investigator should be aware of, and should comply with, the principles of GCP and the applicable regulatory requirements. A record of GCP training should be accessible for all investigators.
4. The investigator/site should permit monitoring and auditing by the Sponsor, and inspection by the appropriate regulatory authority
5. The investigator should maintain a delegation log of appropriately-qualified persons to whom the investigator has delegated significant trial-related duties.
6. The investigator should sign an investigator statement, which verifies that the site is willing and able to comply with the requirements of the trial.

#### 2.1.2 ADEQUATE RESOURCES

1. The investigator should be able to demonstrate a potential for recruiting the required number of suitable subjects within the agreed recruitment period (that is, the investigator regularly treats the target population).
2. The investigator should have sufficient time to properly conduct and complete the trial within the agreed trial period.
3. The investigator should have available an adequate number of qualified staff and adequate facilities for the foreseen duration of the trial to conduct the trial properly and safely.

4. The investigator should ensure that all persons assisting with the trial are adequately informed about the protocol, the investigational product(s), and their trial-related duties and functions.
5. The site should have sufficient processes in place to manage the use of a genetically modified organism containing IMP at the site.
6. The site should have sufficient data management resources to allow prompt data return to the MRC CTU. Sites that have previously participated in MRC CTU-co-ordinated trials should have a proven track record of good data return.

## 2.2 APPROVAL AND ACTIVATION

Each selected clinical trial site must apply for their local R&D approval. The Principal investigator will be required to sign an Investigator Statement which verifies that the site is willing, and able to comply with the requirements of the trial. In addition and in compliance with the principles of GCP, all site staff participating in the trial must complete the Signature and Delegation of Responsibilities Log and forward this to the RIVER Co-ordinating Centre. The RIVER Co-ordinating Centre must be notified of any changes to trial personnel and/or their responsibilities. An up-to-date copy of this log must be stored in the Trial Master File (TMF) at the site and also at the RIVER Co-ordinating Centre. A clinical trial agreement will also be signed by the NHS Trust or Board. Local laboratory normal ranges must also be provided.

On receipt of all necessary approvals, written confirmation will be sent to the principal investigator. The site's pharmacist will also be informed of the site's activation and an initial drug order will be placed by the named pharmacist.

1. The site should conduct the trial in compliance with the protocol as agreed by the Sponsor, by the regulatory authority, and the REC.
2. The principal investigator or delegate should document and explain any deviation from the approved protocol, and communicate this with the trial team at the RIVER Co-ordinating Centre.

## 3 SELECTION OF PARTICIPANTS

RIVER aims to recruit participants from 2 different cohorts:

- **Cohort I – Recently diagnosed**  
Recently diagnosed with primary HIV-1 infection. Participants must be enrolled within 4 weeks of a confirmed diagnosis of primary HIV-1 infection. Participants are first screened and if eligible are enrolled at week 0 when combination ART preferably including raltegravir begins. Randomisation occurs after assessment of eligibility at week 22 (see [Section 3.3](#))
- **Cohort II - Previously diagnosed**  
Previously diagnosed with primary HIV-1 infection. Confirmed diagnosis of primary HIV-1 infection must be within a maximum of 2 years prior to randomisation. Participants must have started at least 3-drug ART within 4 weeks of a confirmed diagnosis and remained on ART since starting. Participants are first screened and if eligible are randomised (see [Section 3.4](#) for full randomisation criteria)

The criteria for primary HIV-1 infection are the same across both cohorts.

The eligibility criteria are the standards used to ensure that only medically appropriate participants are considered for this study. Participants not meeting the criteria should not join the study. For the safety of the participants, as well as to ensure that the results of this study can be useful for making treatment decisions regarding other participants with similar diseases, it is important that no exceptions be made to these criteria for enrolment and randomisation to the study.

### 3.1 NUMBER OF PARTICIPANTS

The study aims to enrol 60 individuals overall from 6 UK centres (both cohorts combined).

Where participants withdraw consent for participation, or are deemed lost to follow-up after randomisation, they will not be replaced. Cohort I participants who do not have an undetectable HIV RNA viral load (<50copies/mL or <200copies/mL for the Taqman Roche 2.0 assay) at week 22 bloods (even after repeat testing) will not be randomised. In such cases, participants will discontinue participation in RIVER. Study participants enrolled into Cohort I that are subsequently ineligible for randomisation or those from either cohort who withdraw consent will be managed as per standard of care (SOC) and no further data will be collected for the study. If study supplied raltegravir is being used, this will no longer be supplied to such patients, although the drug might be continued as part of SOC at the discretion of the treating clinician.

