#### 7.4.1.E NOTIFICATION

The RIVER Co-ordinating Centre should be notified by the investigator of all SAEs within **24 hours** of the investigator becoming aware of the event.

Investigators should notify the RIVER Co-ordinating Centre of any SAEs from the point the participant is recruited into the study. For Cohort I – Recently diagnosed participants investigators should notify the RIVER Co-ordinating Centre of any SAEs occurring from the time of enrolment until 12 weeks after the participant's last study visit (up until post-randomisation week 30). For Cohort II – Previously diagnosed participants investigators should notify the RIVER Co-ordinating Centre of any SAEs occurring from the time of randomisation until 12 weeks after the participant's last study visit

(up until post-randomisation week 30). Any subsequent events that may be attributed to treatment should be reported to the MHRA using the yellow card system.

Having reviewed and checked SAEs, the RIVER Co-ordinating Centre will then be responsible for reporting these to the sponsor within 7 days.

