#### 7.4.2 NOTIFICATION PROCEDURE

1. The SAE Form must be completed by an investigator (a consultant named on the Signature List and Delegation of Responsibilities Log who is responsible for the participant's care), with due care being paid to the grading, causality and expectedness of the event as outlined above. In the absence of the responsible investigator, the form should be completed and signed by a member of the site study team and faxed or emailed as appropriate. The responsible investigator should subsequently check the SAE Form, make changes as appropriate, sign and then re-fax to the RIVER Co-ordinating Centre as soon as possible. The initial report must be followed by detailed, written reports as appropriate.

The minimum criteria required for reporting an SAE are the study number, name of investigator reporting, the event, and why it is considered serious.

2. The SAE Form must be sent by fax to the RIVER Co-ordinating Centre [contact] or password-protected email to [[contact]](mailto:[contact])
3. Follow-up: participants must be followed up until clinical recovery is complete and laboratory results have returned to normal or baseline, or until the event has stabilised. Follow-up should continue after completion of protocol treatment if necessary. A further SAE Form, indicated as 'Follow-up' should be completed and faxed to the RIVER Co-ordinating Centre as information becomes available. Extra, annotated information and/or copies of test results may be provided separately. The participant must be identified by study number, 3 letter code and year of birth only. The participant's name should not be used on any correspondence and should be deleted from any test results.
4. Staff should follow their institution's procedure for local notification requirements.

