### 11.1 COMPLIANCE

The end of the interventional phase of the study is defined as being 12 weeks after each participant's last visit and investigators should continue to notify the RIVER Co-ordinating Centre of all SAEs for this period. After this time the participant's long-term follow-up phase will commence ([Section 6.9](#)). The study will end after the last participant completes their 5th annual visit.

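### Protocol 3.1 ends data collection for Cohort I participants enrolled but not randomised, in conflict with the 12-week SAE notification in 7.4.1.E and 11.1, so some SAEs may go unreported

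*Protocol*

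**What the plan says.** Protocol 3.1 deals first with Cohort I participants whose viral load is still detectable at week 22 after any repeat tests: "In such cases, participants will discontinue participation in RIVER". It then sets one rule for two groups: Cohort I participants enrolled but later ineligible for randomisation on any ground, and participants of either cohort who withdraw consent. Both "will be managed as per standard of care (SOC) and no further data will be collected for the study". No exception for SAEs is given.

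The safety sections say something different.

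- Protocol 7.4.1.E opens with a general duty: "Investigators should notify the RIVER Co-ordinating Centre of any SAEs from the point the participant is recruited into the study". For Cohort I it asks for "any SAEs occurring from the time of enrolment until 12 weeks after the participant's last study visit", followed by a bracket, "up until post-randomisation week 30".
- Protocol 11.1 ends the interventional phase 12 weeks after each participant's last visit and says that "investigators should continue to notify the RIVER Co-ordinating Centre of all SAEs for this period".
- Protocol 7.4.2 requires follow-up after an SAE until recovery and return of laboratory values to normal or baseline, or until the event is stable. It adds: "Follow-up should continue after completion of protocol treatment if necessary".

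Protocol 7.1.1 lists raltegravir and the cART backbone among the investigational products. SAP 2.3 has SAEs collected before randomisation, and SAP 4.8 presents pre-randomisation events overall.

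**The concern.** A Cohort I participant who is not randomised has normally spent 22 weeks or more on cART within the trial. When ineligibility is established, the site holds two instructions: 3.1 tells it to collect nothing more, and 7.4.1.E and 11.1 tell it to notify SAEs for a further 12 weeks. No section says which one governs.

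The people concerned are a selected group. Under 3.3.3, randomisation can fail on platelets, eGFR, haemoglobin, ALT, uPCR, QTc or physical findings, as well as on viral load. Reporting could therefore stop just after an abnormality has been found. Section 3.1 also ends the supply of study raltegravir at that point, so treatment may be changing as well.

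The second half of the rule matters too. Withdrawal of consent can occur in either cohort and in Arm B after vaccine or vorinostat, and 3.1 does not say what happens to an SAE that is open on that day. Section 5.10 distinguishes withdrawing consent to the intervention medication from withdrawing from all stages of the study. The sentence in 3.1 that stops data collection does not.

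**Working it through.** **1. The plan's own end date.** The last scheduled visit for a randomised participant is PR18 (Protocol 6). Adding the 12 weeks of 7.4.1.E gives 18 + 12 = PR30. This matches the bracket, which is therefore correct for randomised participants.

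**2. The same rule for a participant never randomised.** The last visit is week 22 if nothing is repeated (3.3.3).

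| Rule | SAE notification ends | Weeks after last visit |
|---|---|---|
| 7.4.1.E and 11.1 | 22 + 12 = study week 34 | 12 |
| 3.1, read literally | when ineligibility is established | about 0 |

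The gap is up to 12 weeks per participant. If the viral load test or the whole week 22 visit is repeated, as 3.3.3 allows, the end date moves later. The protocol does not say which visit then starts the 12 weeks.

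**3. Is the duty in 7.4.1.E confined to randomised participants?** The bracket fits only them. However, the Cohort I window opens at enrolment and the Cohort II window opens at randomisation. The pre-randomisation period of Cohort I was therefore included on purpose. Section 11.1 refers to each participant's last visit, without restriction.

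**4. How many people?** Protocol 9.3 plans 60 enrolled and bases power on 52.

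- Allowance: 60 − 52 = 8, and 8/60 = 13.3%.
- The allowance covers everyone not reaching PR16/18, that is, Cohort I participants not randomised plus withdrawals. The documents do not split it.

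**5. How many events?** The documents give no SAE rate, so the per-person 12-week risk p below is an assumption. Taking all 8 as affected gives the upper end of what the allowance implies. The chance of at least one SAE is 1 − (1 − p)^8, and the expected number is 8p.

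| Assumed p | Chance of at least one SAE | Expected SAEs |
|---|---|---|
| 1% | 7.7% | 0.08 |
| 2% | 14.9% | 0.16 |
| 5% | 33.7% | 0.40 |

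**6. Effect on power.** With 26 per arm, SD 0.4 and correlations 0.5 and 0.7, the ANCOVA SD is 0.4 × √((1 + 0.7)/2 − 0.5²) = 0.310. Power is then 93.9% for a 50% reduction and 85.6% for a 45% reduction, in line with the stated 94% and 86%. None of these inputs depends on the SAE rule.

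**The case against.** The strongest reply is that this is a question of scope. The bracket in 7.4.1.E makes sense only after randomisation. Section 11.1 leads on to long-term follow-up, and Section 6 ties the visits up to PR18 to randomised participants. On this view the 12-week window was written for randomised participants, and 3.1 is the specific rule for the rest. This stands in part: the bracket does show that the never-randomised were not in mind when the end date was written. It does not settle the matter, because 7.4.1.E starts the Cohort I window at enrolment, and neither it nor 11.1 excludes anyone. On the scope reading, the never-randomised still have a stated start to SAE reporting and no stated end other than the stop in 3.1.

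A reader might infer that late serious events are certain to be lost. The documents do not support that. Nothing in 3.1 revokes the duty in Section 7, so events are missed only where a site lets 3.1 prevail, and 7.4.2 still requires follow-up of an SAE. The yellow-card route in 7.4.1.E is only a limited safeguard. It applies to later events that may be attributed to treatment, and the report goes to the regulator.

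It is also fair to say that those never randomised received no vaccine and no vorinostat. Their regimen is any guideline-recognised ART (5.3), and 11.2.1 describes immediate ART in primary infection as routine. How many used study-supplied raltegravir is not stated; the protocol says only that it is preferred.

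**Conclusion.** The conflict is real and should be resolved. Section 3.1 gives an instruction on SAE data that, taken at its word, is opposite to 7.4.1.E and 11.1 and does not fit 7.4.2. The window in 7.4.1.E has no usable end date for participants never randomised. At sites that follow 3.1, SAEs in up to 12 weeks after the last visit may go unreported in participants exposed to cART.

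The size is small and cannot be fixed from the documents. It would be wrong to read 8 of 60 (13%) as the number of non-randomised participants affected, because that planned allowance also contains withdrawals, including those after randomisation. The chances of 7.7% to 33.7% rest on assumed risks of 1% to 5% and on all 8 being affected.

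Participants never randomised enter no comparison between arms. The primary comparison of total HIV DNA and its power are unaffected. What is at stake is the completeness of safety reporting.

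**What to change.** Reconcile the sections in one amendment.

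- **Protocol 3.1:** add that, for participants enrolled but not randomised, SAEs continue to be notified until 12 weeks after their last study visit, counting any repeat of the week 22 visit, and that SAEs still open are followed as in 7.4.2, to recovery or stabilisation.
- **Protocol 7.4.1.E:** beside the PR week 30 bracket, add the matching end date for participants never randomised.
- **Protocol 3.1, withdrawals:** limit the stop on data to participants who withdraw consent to data collection, in line with the distinction in 5.10, and state how an SAE already open at withdrawal is handled.

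The cost is a short amendment and a few extra SAE contacts. Sample size, treatment rules and the primary analysis do not change.

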### 3.2 CONSENT PROCESS

Eligible individuals will be flagged by a clinical pathway at each clinical site. This is to incorporate one or more of the following:

- Direct referral from participants following recent diagnosis of HIV
- The study will be advertised through NGO, advocacy partners such as THT, HIV ibase, GMFA and through the CHERUB website
- Virology laboratories where recent infection is identified will notify lead clinical principal investigators to follow up with potentially eligible study participants.

- Clinical referrals pathways will be made from colleagues and from other sites where enrolment is not currently planned - through BHIVA, MRC CTU website and clinical networks

For Cohort II several of the clinical sites participating in RIVER have been recruiting individuals into a separate observational cohort study called HEATHER (funded through NIHR BRC and MRC senior fellowship). The HEATHER (REC reference: 14/WM/1104) study has enrolled individuals with confirmed PHI according to similar criteria to those that define PHI for the RIVER study, all of whom commenced and remained on combination ART from the time of PHI. Individuals who enrol into RIVER Cohort II will cease blood draws and clinical follow up through HEATHER for the time they are in the RIVER protocol. They may return to the HEATHER study after completion of the RIVER protocol.

Written informed consent to enter into the study and be randomised must be obtained from participants after explanation of the aims, methods, benefits and potential hazards of the study and BEFORE any study-specific procedures are performed or any blood is taken for the study (sample participant information leaflet is available in [Appendix VII](#)). Separate Participant Information Leaflets and consent forms have been developed for each cohort.

It must be made completely and unambiguously clear to the participant that they are free to refuse to participate in all or any aspect of the study, at any time and for any reason, without incurring any penalty or affecting their treatment.

Signed consent forms must be kept by the investigator and documented in the case report form and copies given to the participant and the RIVER Co-ordinating Centre. With consent, a letter should be sent to the general practitioner informing him/her of the study and the participant's involvement in it; unless the participant expresses on the consent form that they do not wish their GP to be informed (sample GP letter is available in [Appendix VI](#)).

### 3.3 COHORT I – RECENTLY DIAGNOSED PARTICIPANTS

Recently diagnosed participants will be considered eligible for enrolment in this trial if they fulfil all the inclusion criteria and none of the exclusion criteria as defined below. Eligible participants are enrolled at week 0.

#### 3.3.1 ENROLMENT INCLUSION CRITERIA

1. Aged  $\geq 18$  to  $\leq 60$  years old
2. Able to give informed written consent including consent to long-term follow-up
3. Should be enrolled within a maximum of 4 weeks of diagnosis of primary HIV-1 infection confirmed by one of the following criteria:
  - a. Positive HIV-1 serology within a maximum of 12 weeks of a documented negative HIV-1 serology test result (can include point of care test (POCT))
  - b. A positive p24 antigen result and a negative HIV antibody test
  - c. Negative antibody test with either detectable HIV RNA or proviral DNA

- d. PHE RITA test algorithm† reported as “Incident” confirming the HIV-1 antibody avidity is consistent with recent infection (within the preceding 16 weeks)
  - e. Weakly reactive or equivocal 4th generation HIV antibody antigen test
  - f. Equivocal or reactive antibody test with <4 bands on western blot
4. Adequate haemoglobin (Hb $\geq$ 12g/dL for males,  $\geq$ 11g/dL for females)
  5. Weight  $\geq$ 50kg‡
  6. Willing to be treated with cART (preferably including raltegravir) and be randomised to continue cART alone or cART plus intervention (HIV vaccines plus HDACi)
  7. Willing and able to comply with visit schedule and provide blood sampling.

### 3.3.2 ENROLMENT EXCLUSION CRITERIA

1. Women of child bearing potential (WCBP)§
2. In women with intact ovaries and no uterus, any planned egg donation anytime in the future to a surrogate
3. Intention to donate sperm or father a child within 6 months of the intervention
4. Co-infection with hepatitis B (surface antigen positive or detectable HBV DNA levels in blood) or hepatitis C (HCV RNA positive or HCV antigen positive)
5. Any current or past history of malignancy
6. Concurrent opportunistic infection or other comorbidity or comorbidity likely to occur during the trial e.g. past history of ischaemic or other significant heart disease, malabsorption syndromes, autoimmune disease
7. Any contraindication to receipt of BHIVA recommended combination antiretrovirals
8. HIV-2 infection
9. Known HTLV-1 co-infection
10. Prior immunisation with any experimental HIV Immunogens (including any component of the vaccines used in the RIVER protocol; simian or human adenoviral vaccine; other experimental HIV vaccines)
11. Current or planned systemic immunosuppressive therapy (inhaled corticosteroids are allowed)
12. Any history of proven thromboembolism (pulmonary embolism or deep vein thrombosis)

---

† using current cut-offs for optical density as defined by PHE

‡ females aged <20 years of age, and weighing <65kg and <168cm in height will need to have an estimation of blood volume (EBV) >3500mL prior to enrolment. This circumstance is unlikely to arise as most women between the ages of 18 to 20 years would be of child-bearing potential (CBP) and excluded on that basis.

§ defined as any female who has experienced menarche and who has not undergone successful surgical sterilisation (hysterectomy or bilateral oophorectomy) or is not postmenopausal (defined as amenorrhoea  $\geq$  12 consecutive months; or women on hormone replacement therapy (HRT) with documented serum follicle stimulating hormone (FSH) level > 35mIU/mL); NB bilateral tubal ligation is reversible, a women with only tubal ligation who does not meet any of the other criteria is considered a WCBP

13. Any inherited or acquired bleeding diathesis including gastric or duodenal ulcers, varices
14. Concurrent or planned use of any drugs contraindicated with vorinostat i.e. antiarrhythmics; any other drugs that prolong QTc; warfarin, aspirin, sodium valproate
15. Prior intolerance of any of either the components of the vaccine or HDACi,
16. Uncontrolled diabetes mellitus defined as an HBA1C>7%
17. Any congenital or acquired prolongation of the QTc interval, with normal defined as  $\leq 0.44s$  ( $\leq 440ms$ )
18. Participation in any other clinical trial of an experimental agent or any non-interventional study where additional blood draws are required; participation in an observational study is permitted
19. Allergy to egg
20. History of anaphylaxis or severe adverse reaction to vaccines
21. Planned receipt of vaccines within 2 weeks of the first trial vaccination administered at PR week 00 (including vaccines such as yellow fever; hepatitis B, influenza)
22. Abnormal blood test results at screening including
  - a. Moderate to severe hepatic impairment as defined by Child-Pugh classification
  - b. ALT >5xULN
  - c. Platelets <150x10^9/L
  - d. eGFR <60\*\*
  - e. uPCR >30 mg/mmol
23. Physical and laboratory test findings: Evidence of organ dysfunction or any clinically significant deviation from normal in physical examination and/or vital signs that the investigator believes is a preclusion from enrolment into the study
24. Active alcohol or substance use that, in the Investigator's opinion, will prevent adequate adherence with study requirements
25. Insufficient venous access that will allow scheduled blood draws as per protocol

